5.3.2 Health care resource utilisation

Health care resource utilisation will be evaluated within 12 months before cohort entry but not including the index date. The variables listed in [Table 7](#) will be used to capture the utilisation of health care resources. Additional details on the definition of the variables in each data source are described in Section [9.2](#).

Table 7 Health care resource utilisation variables

Health care resource parameter	Definition and categories	Medications included
All dispensings	Number of dispensings for all medications; ordinal variable with 0, 1-9, 10-19, 20 or more	All medications included in Annex Table 1-6
Dispensings for respiratory medications ¹	Number of dispensings for respiratory medications; ordinal variable with 0, 1-4, 5-9, 10 or more	All medications included in the section on respiratory medications in Annex Table 1-6
Dispensings for systemic glucocorticosteroids	Number of dispensings for systemic glucocorticosteroids; ordinal variable with 0, 1-4, 5-9, 10 or more	ATC code H02AB
Dispensings for LABAs	Number of dispensings for LABAs; ordinal variable with 0, 1-4, 5-9, 10 or more	ATC codes R03AC012 (salmeterol) and R03AC013 (formoterol)
Hospitalisations	Number of hospitalisations for any cause; ordinal variable with 0, 1, 2, 3-4, 5 or more	To be determined by each data source
Hospitalisations for COPD	Number of hospitalisations with a primary discharge diagnosis of COPD; ordinal variable with 0, 1, 2, 3-4, 5 or more	ICD-10 codes for COPD: J41-J44, or as defined in Section 5.1 for each data source, but limited to inpatient codes
Hospitalisations for asthma	Number of hospitalisations with a primary discharge diagnosis of asthma; ordinal variable with 0, 1, 2, 3-4, 5 or more	ICD-10 codes for asthma: J45, J46, or as defined in Section 5.1 for each data source, but limited to inpatient codes

ATC = Anatomical Therapeutic Chemical; COPD = Chronic Obstructive Pulmonary Disease; ICD-10 = *International Statistical Classification of Diseases and Related Health Problems, 10th Revision*; LABA = Long-Acting Beta2-Agonist.

¹ Study medications will be counted (e.g., when describing the olodaterol cohort, the dispensings of indacaterol will be counted and vice versa).

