## **8. RESEARCH QUESTION AND OBJECTIVES**

This study aims to assess the use of single-agent olodaterol in clinical practice. The single agent indacaterol, the only marketed LABA authorised in clinical practice for COPD but not for asthma, will also be assessed. Study objectives are as follows:

Primary objectives:

- Quantify the frequency of off-label use of olodaterol among new users of these medications (i.e., the proportion of new users who do not have COPD)
- Describe the baseline characteristics of new users of olodaterol

Secondary objectives:

- Quantify the frequency of off-label use of indacaterol (a LABA approved for COPD but not for asthma) among new users of these medications (i.e., the proportion of new users who do not have COPD), in order to put into perspective the results for olodaterol initiators
- Describe the baseline characteristics of new users of indacaterol

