5.1 MAIN OUTCOMES

The main outcome of the study is the prevalence of off-label prescribing among new users of olodaterol. As a secondary outcome, the prevalence of off-label prescribing among new users of indacaterol will be assessed.

According to age and the presence of a recorded diagnosis of COPD and/or asthma, new users of olodaterol and new users of indacaterol will be classified into the following categories ([Table 4](#)):

- On-label prescribing: adults (aged ≥ 18 years at the index date) with a recorded diagnosis of COPD, with or without asthma
- Off-label prescribing:
 - Adults (aged ≥ 18 years at the index date) with a recorded diagnosis of asthma and without a recorded diagnosis of COPD, and
 - All children (aged < 18 years), irrespective of whether they have a recorded diagnosis of COPD (unlikely), asthma, or other respiratory disease
- Potential off-label prescribing: adults (aged ≥ 18 years) without a recorded diagnosis of COPD or asthma:
 - To further characterise these patients, recorded diagnosis of “other respiratory comorbidities” among these patients will be described (see conditions included in [Section 5.3.4](#)). The possibility of these patients having “probable COPD” will also be

Proprietary confidential information © 2017 Boehringer Ingelheim International GmbH or one or more of its affiliated companies

explored. Probable COPD will be defined by the presence of at least two prescriptions of long-acting beta2-agonist (LABA), long-acting muscarinic antagonist (LAMA), or inhaled glucocorticosteroid (ICS) (or combination) after the age of 40 years but not before (see lists of medications in [Annex Table 1-6](#)).

Table 4 Classification of patients according to age and indication of olodaterol and indacaterol

Recorded diagnosis ¹	Age	On-label prescribing: indication of COPD	Off-label prescribing	Potential off-label prescribing
COPD	≥18	Yes		
COPD and asthma	≥18	Yes		
Children, irrespective of any recorded diagnosis	<18		Yes	
Asthma (no COPD)	≥18		Yes	
No COPD, no asthma ²	≥18			Yes

COPD = Chronic Obstructive Pulmonary Disease.

- 1 Diagnosis recorded at any time before or on the index date and up to 30 days after the index date.
- 2 To further characterise adult patients with no COPD and no asthma, “potential COPD” and “other respiratory conditions” will be described among these patients.

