Very severe	Occurrence of at least one of the following events in the 12 months before the index date unless another time period is specified: 
 • Dispensed oxygen therapy^{1,2} • Dispensed nebuliser therapy^{1,2} • Diagnosis of emphysema at any time before the index date¹

COPD = Chronic Obstructive Pulmonary Disease.

- 1 Severity criteria also included in definition from Curkendall et al., 2006 [[P07-09136](#)].
- 2 Severity criteria also included in definition from Soriano et al., 2001 [[R08-1492](#)].
- 3 Severity criteria modified to align with the Global Initiative for Chronic Obstructive Lung Disease (GOLD) 2016 definition for severity categories C and D [[P16-00121](#)]. If two or more of these criteria occur within a 21-day time period, they will be considered part of the same exacerbation episode and counted only once. If one or more of these criteria occur within a 21-day period of a hospitalisation for COPD, this will be considered part of the same “COPD exacerbation with hospitalisation” episode.

Sources: modified from Verhamme et al., 2012 [[P11-13226](#)]; Soriano et al., 2001 [[R08-1492](#)]; Curkendall et al., 2006 [[P07-09136](#)]; and GOLD, 2016 [[P16-00121](#)].

Because data on hospitalisations are not available in the IMS RWE LPD database, COPD severity will not be described in this database.

The proposed operational definitions to be applied when assessing the severity of COPD are as follows:

- Same-class “drugs for obstructive airways disease”: medications listed in [Annex Table 1-6](#) will be identified through prescriptions/dispensings for the list of medications of interest recorded in the database within 12 months before or on the index date and classified into one of the following drug classes:
 - Bronchodilators: inhaled short-acting muscarinic antagonists (SAMAs), inhaled LAMAs, inhaled short-acting beta2-agonists (SABAs), inhaled LABAs, and fixed combinations of SABAs and SAMAs
 - Inhaled glucocorticosteroids: ICS alone, fixed combinations of SABAs and ICSs, and fixed combinations of LABAs and ICSs
 - Systemic glucocorticosteroids
 - Systemic beta2-agonists
 - Xanthines
 - Roflumilast
- Hospitalisation for COPD exacerbation: an inpatient (primary or secondary discharge) code for COPD (ICD-10 codes: J41-J44), acute bronchitis (ICD-10 codes: J20, J21, J22, J40), or pneumonia (ICD-10 codes J09, J18) within 12 months before or on the index date.

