6.5 HANDLING OF MISSING DATA AND OUTLIERS

The extent of missing data will be evaluated and described. Due to the nature of this study, no imputation of missing data is planned. Missing values are expected in some sociodemographic variables depending on the definition used and in variables related to exposure characterisations such as strength or daily dose. Degree of missingness will depend on the database, and some data sources will have variables that are not available, such as oxygen therapy in PHARMO and hospitalisations in IMS RWE LPD. Diagnoses, prescriptions, and dispensings can be identified in the databases only if they are recorded. Thus, all patients with a certain diagnosis/dispensing in the database will be coded as having

Proprietary confidential information © 2017 Boehringer Ingelheim International GmbH or one or more of its affiliated companies

the respective condition/exposure to the respective drug. All others will be coded as not having the disease/not being exposed to the drug. Therefore, uncoded diagnoses/dispensings may result in misclassification and not in missing values.

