7.5 MAIN ANALYSES

7.5.1 Clinical indication and evaluation of off-label and potential off-label use

A detailed description of the definition of COPD indication and on-label and off-label use is presented in Section [5.1](#). The prevalence of on-label and off-label new users and 95% confidence interval will be presented for olodaterol and indacaterol. Confidence intervals will be calculated using the Clopper-Pearson method for the binomial distribution [[R06-1080](#)]. Patients will be classified hierarchically:

- 1. All children will be classified as off-label, irrespective of their diagnosis.
- 2. All adult patients with a diagnosis of COPD will be considered on-label irrespective of whether they have a diagnosis of asthma or any other respiratory condition.
- 3. All adults without a COPD diagnosis and with a diagnosis of asthma will be classified under the group of “asthma only,” irrespective of whether they have any other respiratory condition. These patients will be classified as off-label.
- 4. All adults with no COPD and no asthma diagnosis will be classified as potential off-label. Among these patients, “probable COPD” and “other respiratory conditions” will be described. These will not be mutually exclusive, patients can have one or more of the respiratory conditions listed and “probable COPD.” Patients with no “other respiratory conditions” and no “probable COPD” will be classified under “No history of recorded respiratory conditions and no probable COPD.”

Results for the main analysis will be presented overall (Shell Table 10.1) and separated by age group (< 18, 18-29, 30-39, 40-49, 50-59, 60-69, 70-79, 80+ years; Shell Tables 10.2 through 10.9).

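### SAP Annex Table 1-6 files indacaterol as a SABA and omits olodaterol, so variables built from it count prior use of the other study drug in one cohort but not in the other

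*SAP*

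**What the plan says.** Protocol Section 8 describes the comparator as "The single agent indacaterol, the only marketed LABA authorised in clinical practice for COPD but not for asthma". SAP Annex Table 1-6 nevertheless has indacaterol, R03AC18, as the last row under inhaled SABAs. Its inhaled LABA group holds only salmeterol (R03AC12) and formoterol (R03AC13). Olodaterol, coded R03AC19 in SAP Table 10, has no row anywhere in the annex.

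The annex is the working list for several baseline variables:
- Comedications (SAP 5.3.6 and 7.2) are those listed in the annex.
- The severity drug classes (SAP 5.3.3) start from annex medications, which "will be identified through prescriptions/dispensings for the list of medications of interest". SABAs and LABAs are then pooled in one bronchodilator class.
- The 'All dispensings' row of Table 7 (SAP 5.3.2) is defined as "All medications included in Annex Table 1-6", and the respiratory row by the respiratory section of the same annex.
- 'Probable COPD' (SAP 5.1) requires "at least two prescriptions of long-acting beta2-agonist (LABA), long-acting muscarinic antagonist (LAMA), or inhaled glucocorticosteroid (ICS" or combination, after age 40 and not before, with the annex as the medication list.

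Table 7 footnote 1 says that study drugs are counted: "when describing the olodaterol cohort, the dispensings of indacaterol will be counted and vice versa". It is marked only on the respiratory row. The LABA row of Table 7 is specified as "ATC codes R03AC012 (salmeterol) and R03AC013 (formoterol".

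The medication window is stated in two ways. The operational definitions in SAP 5.3.3, and SAP 5.3.6, include the index date. SAP Section 5, Table 8 and Section 7.2 refer to the period before it. SAP 5.3.2 (resource utilisation) explicitly excludes it.

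**The concern.** Describing olodaterol initiators at baseline is a primary objective. The same description of indacaterol initiators is a secondary objective, and the indacaterol off-label results are there to put those for olodaterol into perspective. If one list captures prior indacaterol and misses prior olodaterol, a difference between the two baseline tables can come from the code list and not from the patients. SAP 6.3 allows a patient to enter both groups, so prior use of the other study drug can occur.

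Two related defects sit beside this one. The LABA lists leave out both study drugs, so prior LABA use is undercounted. The conflicting windows decide whether the index dispensing itself is counted, and under the present annex that choice also acts differently in the two cohorts.

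**Working it through.** The plan has no figure of its own to reproduce. The check passes hypothetical patients through the printed code lists.

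**Step 1: four prior dispensings of the other study drug.** The number 4 is assumed. The olodaterol initiator has 4 × R03AC18; the indacaterol initiator has 4 × R03AC19.

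| Variable | Olodaterol initiator | Indacaterol initiator |
|---|---|---|
| Table 7, 'All dispensings' | 4 | 0 |
| Table 7, respiratory row, annex codes only | 4 | 0 |
| Table 7, respiratory row, footnote 1 followed | 4 | 4 |
| Comedications, inhaled SABA group | 4 | 0 |
| Severity, bronchodilator class | 4 | 0 |
| Table 7, LABA row (codes as printed or corrected) | 0 | 0 |
| Annex LABA list | 0 | 0 |
| LABA, LAMA or ICS count for 'probable COPD' | 0 | 0 |

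The asymmetry appears only where the whole annex is used. The LABA row and 'probable COPD' miss both drugs alike. With both codes on the LABA list, the LABA count becomes 4 in each cohort.

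The footnote and the annex cannot both be followed. Under the footnote the indacaterol initiator has 4 respiratory dispensings; by the annex the same patient has 0 dispensings of any kind, so a part exceeds its whole.

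**Step 2: severity.** Moderate needs two dispensings of one class no more than 6 months apart in the 12 months before index; otherwise the patient is Mild. No severe or very severe criterion is met, and the index date is excluded.

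| Prior dispensings | Olodaterol initiator | Indacaterol initiator | R03AC19 added |
|---|---|---|---|
| Other study drug, days −120 and −60 | 2 → Moderate | 0 → Mild | Moderate in both |
| LAMA day −120, other study drug day −60 | 1 + 1 = 2 → Moderate | 1 + 0 = 1 → Mild | Moderate in both |
| Two LAMA plus other study drug | Moderate | Moderate | Moderate in both |

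Filing indacaterol under SABAs does not matter here, because SABAs and LABAs are pooled. The missing olodaterol row does.

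**Step 3: the window.** Take one prior LAMA at day −60 and no other drug.
- Index date excluded: 1 counted in each cohort, both Mild.
- Index date included, annex as printed: the indacaterol initiator has 1 + 1 = 2, Moderate; the olodaterol initiator has 1 + 0 = 1, Mild.

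This difference needs no cross-use.

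**Step 4: 'probable COPD'.** Take a patient over 40 with no recorded respiratory diagnosis and two prior dispensings of the other study drug, both after 40. As printed, 0 LABAs are counted and the patient falls into "No history of recorded respiratory conditions and no probable COPD". With both codes listed as LABAs, 2 are counted and the criterion is met. The effect is the same in both cohorts. SAP 5.1 gives no end date for the two prescriptions, so once the study drugs are listed, the index dispensing and one refill (1 + 1 = 2) would also satisfy it.

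**The case against.** The best reply is that the intent is already clear. Footnote 1 wants study drugs counted in both directions, and a sensible programmer would carry that over to the row that contains the respiratory row. Indacaterol has its own annex row, so a drug-level table can show it properly. The extra zeros are evident slips, since the drug names stand beside the codes. The examples need patients with little other bronchodilator use; two LAMA dispensings remove the severity error. The SAP defers to database-specific specifications in Section 9.2 and to table shells in a separate file. Neither was available here, and either may correct the lists locally.

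Most of this stands as a limit on size. It does not make the core list right: the footnote is absent from 'All dispensings', from comedications and from severity, and the annex cannot deliver it for olodaterol even where it is marked.

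Some stronger readings do not stand:
- A reader might infer that the LABA row records the cohorts differently. It gives 0 against 0.
- A reader might take SAP 6.5 ("All others will be coded as not having the disease/not being exposed to the drug") to turn a missing annex row into non-exposure. That section concerns events not recorded in the database; an olodaterol dispensing is recorded.
- A reader might infer from SAP 6.3 that cross-use is expected. It is permitted and will be reported, with no frequency given.
- A reader might conclude that the LABA-naïve and switcher strata are wrong. The SAP names no code list for them, so this cannot be shown.

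**Conclusion.** The code list is wrong as written. In the comedication tables, the 'All dispensings' row and the severity bronchodilator class, prior indacaterol is counted in olodaterol initiators (as a SABA in the comedication list), and prior olodaterol is not counted in indacaterol initiators. This contradicts the intent of footnote 1. Prior LABA use is also undercounted, equally in both cohorts, in the Table 7 LABA row and in 'probable COPD'. The window conflict adds a second differential effect if the index date is included.

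The reach is limited. The on-label/off-label classification rests on age and diagnosis and does not change; only the description within the potential off-label group can. Severity moves only at the mild/moderate boundary and is not described in the French database. No cohort-level percentage follows, because the number of patients using both drugs is not given. The conclusion assumes that the core list is applied as printed, without correction in Section 9.2 or the shells. It is worth correcting because the affected tables serve a primary objective and the repair is small.

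**What to change.** - In Annex Table 1-6, move R03AC18 to inhaled LABAs and add R03AC19 there.
- In the Table 7 LABA row, print R03AC12 and R03AC13 and add R03AC18 and R03AC19.
- Apply footnote 1 to the 'All dispensings' and LABA rows as well.
- State one medication window in Section 5, 5.3.3, 5.3.6, Table 8 and 7.2 that leaves out the index-drug dispensing in both cohorts. Adding R03AC19 alone would restore symmetry, but if the index date stays in, the index drug would still help to define baseline severity.
- In Section 5.1, count only dispensings before the index date for 'probable COPD', since both study drugs would then be LABAs.

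The pooled severity classes in 5.3.3 can stay as they are. The cost is text edits to one annex table, Tables 7 and 8 and the sections named, plus matching code lists at each centre. No new data are needed: both codes are already used to form the cohorts.

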#### 9.3.3.7 Health care resource utilisation

Health care resource utilisation will be evaluated for the **12 months before the index date**.

- Total number of dispensings; all medications included in [Annex Table 4:2](#)
- Total number of dispensings for respiratory medications; all medications included in the section of respiratory medications in [Annex Table 4:2](#)
- Total number of dispensings for systemic glucocorticosteroids; ATC code H02AB
- Total number of dispensings for LABAs; ATC codes R03AC012 (salmeterol) and R03AC013 (formoterol)
- Total number of hospitalisations; number of hospitalisations for any cause
- Total number of hospitalisations for COPD; number of hospitalisations with a primary discharge code for COPD; ICD-10 codes J40-J44; ICD-9 codes: 491, 492, 496
- Total number of hospitalisations for asthma; number hospitalisations with a primary discharge code for asthma; ICD-10 codes J45, J46; ICD-9 code: 493

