7.2 CONCOMITANT DISEASES AND MEDICATION

Frequency of history of specific diseases and conditions of interest at any time before the index date will be assessed for each exposure group in each data source within the overall study population (Shell Table 5.1 and Shell Table 6.1). The same analysis will be repeated for adults (Shell Table 5.2 and Shell Table 6.2) and for those patients aged 40 years or older with a diagnosis of COPD (Shell Table 5.3 and Shell Table 6.3). Diagnosis of COPD, asthma, and other respiratory comorbidities and time since first COPD diagnosis will be included as part of the description of medical history. In this table, COPD, asthma, and respiratory comorbidities will not be mutually exclusive, and a patient will be allowed to be in more than one group. The comorbidities to be considered are listed in Sections [5.3.4](#) and [5.3.5](#), and a complete list of codes is included in [Annex Table 1-5](#).

The number and percentage of patients with a prescription or dispensing for a specific medication within the year before the index date will be described in each exposure group for the overall population (Shell Table 7.1 and Shell Table 8.1), for all adults (Shell Table 7.2 and Shell Table 8.2), and for those patients aged 40 years or older with a diagnosis of COPD (Shell Table 7.3 and Shell Table 8.3). A description of the medications considered is detailed in Section [5.3.6](#), and the list of codes is presented in [Annex Table 1-6](#).

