Annex Table 1-6 (cont'd) Anatomical Therapeutic Chemical codes for comedICATIONS

Medication description	ATC code
Respiratory medications (cont'd)	
Oxygen therapy	V03AN01
Nebuliser therapy	ATC codes not available ¹
Cardiovascular medications	All codes listed below in section Cardiovascular medications
Cardiac glycosides and antiarrhythmics, Classes I and III	C01A, C01B
Vasodilators used in cardiac diseases	C01D
Other cardiac preparations	C01B, C01C
Diuretics	C03
Peripheral vasodilators	C04
Beta blocking agents	C07
Calcium channel blockers	C08
Antihypertensives	C02
Agents acting on the renin-angiotensin system	C09
Angiotensin-converting-enzyme inhibitors	C09A, C09B
Angiotensin II receptor antagonists	C09C, C09D
Renin-inhibitors	C09X
Lipid-modifying agents	C10
HMG CoA reductase inhibitors (statins)	C10AA
Other lipid-modifying agents	C10AB, C10AC, C10AD, C10AX
HMG CoA reductase inhibitors (statins), other combination	C10BX
Antithrombotic agents	B01
Platelet aggregation inhibitors	B01AC
Systemic antibacterials	J01
Iron preparations	B03A
Proton pump inhibitors	A02BC
Drugs used in diabetes	A10

Proprietary confidential information © 2017 Boehringer Ingelheim International GmbH or one or more of its affiliated companies

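### SAP Table 7 defines prior LABA dispensings by malformed ATC codes that conflict with the SAP's own annex, and C01B stands in two cardiac rows of that annex; both affect descriptive baseline rows only

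*SAP*

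**What the plan says.** Table 7 in SAP 5.3.2 sets out seven health care utilisation variables for the 12 months before cohort entry, excluding the index date. The LABA row is described as "Number of dispensings for LABAs; ordinal variable with 0, 1-4, 5-9, 10 or more", and its medication cell reads "ATC codes R03AC012 (salmeterol) and R03AC013 (formoterol". Protocol 9.3.3.7 has the same definition: "Total number of dispensings for LABAs; ATC codes R03AC012 (salmeterol) and R03AC013 (formoterol". Below the SAP's introduction to the table stands a pointer: "Additional details on the definition of the variables in each data source are described in Section" 9.2.

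SAP Annex Table 1-6 lists salmeterol as R03AC12 and formoterol as R03AC13 under inhaled LABAs. Protocol Annex Table 4:2 agrees.

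In the cardiovascular part of Annex Table 1-6, the row "Cardiac glycosides and antiarrhythmics, Classes I and III" carries C01A and C01B. The row for other cardiac preparations carries C01B and C01C. The protocol annex has the same two entries. SAP 7.2 says how these rows are reported: "The number and percentage of patients with a prescription or dispensing for a specific medication within the year before the index date". SAP 5.3.6 defines the comedication window as including the index date.

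**The concern.** These are operative code lists, not background text. SAP section 7 has each research centre run its own analysis from the core protocol and SAP. Under protocol 9.6 the coordinating centre receives summary tables only, so it cannot check a code match at record level.

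A failed match would not announce itself as missing data. SAP 6.5 codes any patient without a matching record as unexposed, so a string that matches nothing gives category 0.

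The LABA row is reported by study drug for the whole population, for adults, and for COPD patients aged 40 or older (SAP 7.1.2). It contributes to one of the two primary objectives, the description of new users' baseline characteristics.

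The C01B duplication needs no programming slip: applying the annex as printed puts the same users in two rows.

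**Working it through.** The plan states no figure for this point, so there is none to reproduce. The check compares code lists.

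**LABA codes**

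| Place | Salmeterol | Formoterol | Characters |
|---|---|---|---|
| SAP Table 7 | R03AC012 | R03AC013 | 8 |
| Protocol 9.3.3.7 | R03AC012 | R03AC013 | 8 |
| SAP Annex Table 1-6 | R03AC12 | R03AC13 | 7 |
| Protocol Annex Table 4:2 | R03AC12 | R03AC13 | 7 |

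1. The reference list is 43 substance-level codes taken from the documents: 18 in R03AC (02 to 19), 5 in R03BB, 7 in R03AK, 8 in R03BA, 2 in R03DX, 2 in R03BC, and V03AN01. The sum is 18 + 5 + 7 + 8 + 2 + 2 + 1 = 43. All 43 have seven characters.
2. Exact match of the two Table 7 strings against the list: 0 of 43.
3. Prefix match (a listed code beginning with the string): 0 of 43.
4. Truncation to seven characters: both strings become R03AC01, which is not on the list, so again 0 of 43.
5. With the extra 0 removed, the strings become R03AC12 and R03AC13. Each matches exactly one code, that of the drug named beside it.

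Used literally, the strings therefore find no salmeterol or formoterol dispensing, and SAP 6.5 then places every patient in category 0. Table 7 would also contradict itself. Its respiratory-medication row points to Annex Table 1-6, so a patient with 5 to 9 salmeterol dispensings and no other respiratory drug would fall in category 5-9 in that row and in category 0 in the LABA row.

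**C01B**

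| Code | Glycosides and antiarrhythmics | Vasodilators | Other cardiac preparations | Rows |
|---|---|---|---|---|
| C01A | yes | | | 1 |
| C01B | yes | | yes | 2 |
| C01C | | | yes | 1 |
| C01D | | yes | | 1 |

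Patients in the other row = users of C01B or C01C. Excess over a C01C-only row = users of C01B who do not also use C01C. The excess lies between 0 and the full number of C01B users. The documents give no frequencies, so it cannot be narrowed.

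The cardiovascular total is not inflated if it counts patients with any listed code. The all-dispensings row of Table 7 would count C01B dispensings twice only if it were built by adding up annex rows.

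**Reach.** SAP 5.1 and 7.5.1 classify on-label, off-label and potential off-label use from age and recorded diagnoses. COPD severity (5.3.3) and probable COPD (5.1) take their drug lists from Annex Table 1-6, not from the LABA row of Table 7. Neither defect enters the off-label classification.

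**The case against.** The strongest reply is that this is a spelling slip with its correction in the same document. The drug names stand in the cell, the well-formed codes are in Annex Table 1-6, and Table 7 defers to Section 9.2 for database-specific definitions. That section is not in the text available for this review and may already hold usable codes. In France, medications are mapped from EphMRA to ATC before any matching. An all-zero row would also be conspicuous beside the switcher stratum and the comedication tables, and the interim report runs every planned analysis before the final one.

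Most of this stands. A reader might infer that the row will be zero for everyone. The documents do not support that; they support only that it would be zero if the strings were copied literally. A reader might also infer that the codes do not exist in the ATC system. The ATC index is not in the documents, so all that can be shown is that they match no code there. Nor is this row the only measure of prior LABA use: the LABA-naïve and switcher strata and the comedication tables also capture it.

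On C01B, it is fair to say that nothing in the plan requires comedication rows to be mutually exclusive. But no reason is given for placing one code in both a named group and a group labelled other. The documents do not show whether the second entry is surplus or a misprint.

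These points limit the consequence. They do not reconcile Table 7 with the annex, and the LABA strings passed unchanged from the protocol into the SAP.

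**Conclusion.** Both defects are real and should be corrected before the tables are programmed or, if they already have been, checked against the programs. For the LABA row, the share of salmeterol and formoterol dispensings missed is 100% if the strings are used literally and 0% if the centres use the names, the annex, or corrected codes in Section 9.2. The documents do not show which applies. For C01B, every user is counted in a second row if the annex is applied as printed; the number of patients is unknown.

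The effect is confined to descriptive baseline rows. It would be wrong to read this as a threat to the prevalence of off-label use.

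A separate question remains after the spelling is corrected. The row would still cover only salmeterol and formoterol, and not the LABA/ICS combinations R03AK06 to R03AK12 that the SAP annex lists. This point does not settle which products belong in the row.

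**What to change.** 1. In SAP Table 7, replace the two codes with R03AC12 and R03AC13, or refer to the LABA section of Annex Table 1-6. Make the same change in protocol 9.3.3.7 at its next revision.
2. Confirm whether C01B under other cardiac preparations is surplus or a misprint for another code, then keep C01B in one row only. Apply this to SAP Annex Table 1-6 and protocol Annex Table 4:2.
3. Add a program check of the Table 7 LABA row against the salmeterol and formoterol comedication rows. Table 7 excludes the index date and SAP 5.3.6 includes it, so exact equality is not the test. Every patient with at least one dispensing in Table 7 should appear in the comedication rows, and any additional comedication patient should have such a dispensing only on the index date.

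The cost is a few table cells, one query about C01B, and one check per centre. No new data and no change of design are needed.
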